[name]
Chirurgia Generale ed Oncologica
Ospedale Mauriziano "Umberto I", Torino,
Office: [name]
[contact]
e-mail: [contact]

Torino, September 9, 2025

"Resection of the mesentery vs Kono-S anastomosis in preventing surgical recurrence for primary Crohn Disease: the REMEASURE prospective, randomized, controlled trial"

Clinical Trial. Gov number NCT07164209

Remeasure study protocol + statistic

Sincerely

[name]

REsection of the MEsenteric vs Anastomotic configuration and SUrgical REcurrence.

REMEASURE Trial in Crohn's Disease V2.1

Resection of the mesentery with functional end-to-end anastomosis vs Kono-S anastomosis in preventing relapse after ileocolic resection for primary Crohn's Disease.

A prospective, monocentric, randomized trial.

[name]*

* Consultant Surgeon, Division of General and Oncologic Surgery. Department of Surgery.

Ospedale Mauriziano "Umberto I", Torino, Italia.

Office: [name]. [contact]. E-mail: [contact]

Background

Crohn's disease (CD) is an Inflammatory Bowel Disease (IBD), with a relapsing and remitting course, and with an annual incidence of 3–25 per 100000 inhabitants. Over 80% of patients with CD will require a surgical procedure due to abdominal complications within 15 years from diagnosis, and 50% of them will require reoperation for recurrent intestinal disease in the next 15 years^{1,2}.

The gold standard surgical treatment of CD patients, as reported by latest ECCO, ECCO-ESCP, and SICCR guidelines, is based on laparoscopic approach, bowel resection without microscopically disease-free margins, and stapled side-to-side anastomosis³⁻⁵. However, two novelties have recently appeared in the field of CD surgery, both aimed to improve long-term surgical recurrence: the inclusion of the mesentery in the resection of a diseased bowel loop, and a new anastomotic configuration to leave the mesentery far from the anastomotic margins^{6,7}.

At present, the incidence and prevalence, clinical significance, surgical implications, and role in surgical recurrence of mesentery thickening and enlarged lymph nodes are completely unknown. Crohn's disease has been thought to originate in the gut lumen, and thus the medical treatment tends to focus on mucosal inflammation. Surgical treatment is based on the resection of the diseased bowel but, unlike cancer surgery, the removal of the mesentery and associated lymph nodes is not considered essential for adequate treatment⁸. Since a thickened mesentery often bleeds heavily when divided, a common approach among surgeons has been to disconnect it flush with the intestine and to leave it retained. Furthermore, no long-term benefits in terms of recurrence have been reported after mesentery removal. However, recent data suggest that margin positivity and reoperation rates can be substantially reduced if resection is guided by mesenteric based strategies^{9,10}. The mesenteric organ is a single structural entity spanning the gut from duodenojejunal flexure to mesorectum; it is now recognized that this histological overlap is the true intestinal hilum, where blood vessels enter or leave. At the intersection between the intestine and the mesentery, the mesenteric mesothelium continues onto the intestine and contributes to the cellular component of the outer layer, the serosa. From the serosa, connective tissue separations extend into underlying muscle and submucosa, meaning that the mesenteric and intestinal connective tissue are contiguous^{9,10}. Crohn himself was the first to document mesenteric abnormalities, noting that mesenteric fat often advances over the intestinal surface¹¹. Nowadays, the mesentery has been proposed as a separate organ, with a role in systemic inflammation. Visceral tissue plays an important role in immunoregulation and may

function as a pro-inflammatory agent; adipocytes release molecules like adiponectin and leptin are implicated in the production of pro and anti-inflammatory cytokines. Fibrocytes also play a central role in the development of systemic inflammation. In pathological states involving mesenteric inflammation (including CD) circulating fibrocytes levels are elevated, secreting cytokines, favoring antigen presentation and enhancing the production of metalloproteinases¹². The most evident link between the mesentery and Crohn's disease is the macroscopic phenomenon of "fat wrapping" or "creeping fat," where mesenteric fat is inflamed and extends beyond its normal anatomical distribution over the surface of the contiguous intestine. Fat wrapping is a typical and constant finding in Crohn's disease, and is absent in all other forms of intestinal inflammation. The degree of fat wrapping seems to correlate with the severity of intestinal inflammation in the contiguous intestine. Furthermore, some patient presents with extensive lymph nodes enlargement throughout the mesentery tributary of a diseased segment. The reason of this phenomenon and its pathological rule are nowadays completely unknown. In consideration of the above-mentioned evidences, we could target the CD therapy also on the mesentery. At present there are no drugs specifically designed to act on the mesentery, so that the only target-therapy is surgical removal. Mesenteric division in CD is challenging because of bleeding that may be difficult to control^{7,9,13}. Excision of the mesentery is associated with an increased lymphatic tissue removal; this may reduce the immunological stimulation, resulting in improved post-operative outcomes. It may also reduce the recruitment of fibroblasts which subsequently migrate to the intestinal surface⁸. Coffey et al. reported the first retrospective study demonstrating the clinical relevance of including the mesentery in ileocolic resection for CD. The authors analyzed the rate of surgical recurrence after inclusion of the mesentery during ileocolic resection for CD, by comparing two cohorts of patients: cohort A (30 patients who underwent classical ileocolic resection close to the bowel) and cohort B (34 patients in which the affected mesentery was fully dissected and partially excised). As a result, cumulative reoperation rate for CD recurrence were 40% and 2,9% in cohort A and B respectively. In addition, intestinal length and margin positivity rates were both reduced, while nodal yield was increased, following mesenteric resection⁷.

With the same intent of reducing surgical recurrence rate after ileocolic resection of CD, Kono et al. published in 2011 a paper concerning a new technique of an anti-mesenteric, functional end-to-end anastomosis (EEA), called Kono-S anastomosis⁶. After the bowel and the corresponding mesentery have been mobilized, ileal and colonic edges are transected with a linear cutter, with the mesentery

located at the center of the stump; the intervening mesentery is divided close to the bowel, to avoid any devascularization or denervation. The 2 staple lines are approximated to create a kind of supporting column to maintain the anastomosis caliber. Two longitudinal enterotomies, 7 cm long, are made at the antimesenteric side of the 2 bowel stumps, starting from 1 cm from the staple line. A hand-sewn, side-to-side, antimesenteric anastomosis is then performed, approximating the anastomotic ends in a transverse fashion. The endoscopic recurrence rate has been reported to be lower with Kono anastomosis than with conventional EEA, and two studies showed a 5-year surgical anastomotic recurrence rate was 1.8%, during a median follow-up of 65 months (range, 43–138 months)^{14,15}. Shimada et al. published in 2019 a retrospective trial showing that the Kono anastomosis was associated with a low risk of recurrence after 1 year. Kono anastomosis was reported to be superior in terms of anastomotic recurrence at 5 years, using Kaplan–Meyer analysis, as well as having a lower anastomotic leakage rate¹⁶. The first RCT comparing Kono-S anastomosis and standard anastomosis in CD has been recently published. The authors found a significant reduction in postoperative endoscopic recurrence rate, and also a decrease in the severity of endoscopic recurrence score, in favor of the Kono-S technique comparing to a conventional side-to-side anastomosis, performed with a double fire of a linear stapler, and with the transverse staple line buried in a running suture¹⁵. Despite some peculiarities in terms of suturing, the Kono anastomosis is a functional, end- to-end anastomosis which keeps the mesentery distant from the mucosal sutures but leaving in situ the mesentery regardless of its characteristics. In the study by Luglio et al., it was compared with a standard side-to-side anastomosis, but without mesentery removal¹⁵.

Patients who meet inclusion criteria will be randomized between two surgical procedures:

The excision of the mesentery and ileocolic anastomosis (group A) and the Kono-S anastomosis (group B) after ileocolic or ileo-cecal resection. The operation could be performed with open or laparoscopic approach. Two videos will be provided showing the anastomotic techniques in order to improve standardization among the contributing Centers.

- 1) Excision of the mesentery: the mesentery is fully dissected and excised to the limit of macroscopic “fat wrapping”, where mesenteric fat is inflamed and extends beyond its normal anatomical distribution over the surface of the contiguous intestine. A functional, end-to-end, stapled anastomosis between colon and ileum is than performed (the functional end-to-end is a latero-lateral, antiperistaltic, antimesenteric anastomosis, which has a similar, final configuration of the Kono-S).
- 2) Kono-S anastomosis: the mesentery is not removed but cutted close to the bowel. The bowel is then divided transversely by placing a linear stapler perpendicular to the intestinal lumen and the mesentery. The corners of the two staple lines are reinforced and the two stumps are approximated using 5–7 sutures to create the column. If the caliber of the two intestinal segments differs significantly, the sutures should be spaced to evenly distribute the surplus tissue of the larger segment, in order to achieve good approximation and stable support for the anastomosis. To create the anastomosis, an antimesenteric longitudinal enterotomy (or colostomy) is performed on each stump to allow a transverse lumen of 7 cm in diameter for the small bowel or closer to 8 cm for the colon. In this way the supporting column is located immediately behind the posterior wall of the anastomosis providing a rigid and stable support to prevent mechanical deformation and functional constriction of the lumen of the anastomosis.

Study Design for a Randomized Trial

The aim of the study is to determine whether the two therapies have the same efficacy; therefore, we are in the framework of No Difference Testing.^{17 18}

Based on previous literature the expected reduction rate of 6 months for endoscopic recurrence after Kono anastomosis was 25% in order to be more conservative (45% after resection of the mesentery group and 20% in the Kono group), and a value of 0.05 (1-sided) and 75% power was estimated a sample size of 70 patients.

After enrollment, patients will be randomly assigned in a 1 : 1 ratio between Kono anastomosis and resection of the mesentery, by controlling for age, sex, smoking habits, and other health related quantities, including the origin from different centers will be taken into account.

The two Groups will be compared for safety in terms of perioperative characteristics and postoperative complications. Continuous variables will be analysed using a two-tailed, unpaired, Student's t-test, and proportions will be compared using two-tailed, Fisher's exact or chi-square test, where appropriate. Since multiple tests will be performed, a suitable p-value correction will be used, such as Bonferroni correction. A model-based approach for the multivariate analysis, setting the presence of postoperative complications as dependent variable will be performed, a binary logistic regression will be used, with all the variables significant at the univariate level as predictors.

The greatest emphasis will be on the dummy variable encoding the different treatments (for example 1 = "Kono anastomosis", 0 = "Resection of the mesentery"). In this context, the equivalence may be evaluated in two ways: 1 • the associated coefficient of the regression is not significant from a statistical point view. • the Odds Ratio (OR) associated to the corresponding coefficient is close to 1 (and in particular the 95% confidence interval contains 1), meaning that changing the type of treatment does not affect the probability postoperative complications.

Endoscopic, clinical, and surgical recurrences will be analyzed using the time-to-event estimates of the Kaplan-Meier function, and compared for univariate analysis with the Log-rank test. Cox proportional hazard regression analysis will be used to set up a predictive model simultaneously exploring the effects of the independent variables on recurrences in relation to time. Significance will be considered for p-value inferior to 0.05.

Data collection

Data will prospectively be collected using a web-based, dedicated, REDCup database. A local study manager will be identified for each participating center, and a dedicated REDCup username and password will be assigned. The completeness and congruity of the data will be checked periodically by the study's Scientific Committee. The Scientific Committee will refer to the local managers for any request for clarification.

Duration of the study

24 months

Ethical consideration

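### The planned multiplicity correction of the univariate safety comparisons makes an excess of complications harder to detect, in a plan that reads non-significance for complications as equivalence

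*Protocol*

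**What the plan says.** All of this is in the Protocol, section Study Design for a Randomized Trial.

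- The safety paragraph opens: "The two Groups will be compared for safety in terms of perioperative characteristics and postoperative complications". Continuous variables get a two-sided t-test; for the rest, "proportions will be compared using two-tailed, Fisher's exact or chi-square test, where appropriate".
- The next sentence is the one at issue: "Since multiple tests will be performed, a suitable p-value correction will be used, such as Bonferroni correction". Bonferroni is an example. The number of tests is not given.
- A binary logistic regression for postoperative complications follows, "with all the variables significant at the univariate level as predictors". The plan puts most weight on its treatment term. It accepts equivalence if that coefficient is non-significant, or if the odds ratio is near 1 with a 95% CI that includes 1. No correction is stated for this step.
- The recurrence paragraph (Kaplan-Meier, log-rank, Cox) ends: "Significance will be considered for p-value inferior to 0.05".

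Peri-operative safety is one of the two objectives under Aim of the study, and postoperative complications are a secondary endpoint. The sample size rests on endoscopic recurrence alone: "a value of 0.05 (1-sided) and 75% power was estimated a sample size of 70 patients". No expected complication rate and no power for safety are given.

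**The concern.** A familywise correction lowers the risk of false positives at the price of more false negatives. That is a sensible trade when the feared error is a false claim. For complications after two operations in a 70-patient trial, the costlier error is missing a real excess in one arm, and the correction increases it. The longer the list of safety variables, the higher the bar for each of them.

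The reading rule makes this worse. Where non-significance for complications counts as equivalence, any step that makes non-significance more likely also makes a conclusion of equal safety more likely. The correction may also reach the regression indirectly, because predictors are chosen by univariate significance and the text does not say whether the corrected or the uncorrected p-value decides entry.

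At stake is half of the stated aim: a genuine difference in complications could be reported as no difference.

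**Working it through.** **Inputs from the Protocol.** Total 70 patients; allocation "randomly assigned in a 1 : 1 ratio", hence 35 per arm; two-sided Fisher or chi-square tests; nominal level 0.05; Bonferroni as the named example.

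**Inputs the Protocol does not give (assumed).** Number of tests k: 5 to 10, with 2 and 20 as outer values. Complication rates: 10% versus 30% as the base case, with other threefold pairs as the range. No dropout is stated, so all 70 are counted; losses would lower power further.

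**Step 1: reproduce the plan's own figure.** Primary endpoint rates are "45% after resection of the mesentery group and 20% in the Kono group", one-sided 0.05, power 75%. With unpooled variance:

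n per arm = (1.645 + 0.674)² × (0.45×0.55 + 0.20×0.80) / 0.25² = 5.38 × 0.4075 / 0.0625 = 35.1

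That is 70.1 in total before rounding, and power at 35 per arm is 74.9%. The stated 70 is reproduced, and 35 per arm is the right base for the safety calculation.

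**Step 2: exact power for a complication difference.** For all 36 × 36 possible outcomes (i, j) with 35 per arm, the two-sided p-value is computed and

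power = Σ Bin(i; 35, p₁) × Bin(j; 35, p₂) × 1[p-value ≤ 0.05/k]

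Base case, 10% versus 30%:

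| Tests k | Level 0.05/k | Fisher | Chi-square |
|---|---|---|---|
| 1 (no correction) | 0.05 | 45.5% | 56.5% |
| 2 | 0.025 | 35.3% | 46.2% |
| 5 | 0.01 | 21.9% | 30.5% |
| 10 | 0.005 | 15.1% | 21.9% |
| 20 | 0.0025 | 9.9% | 14.9% |

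**Step 3: sensitivity to the base rate.** A threefold ratio does not by itself fix the power. Fisher:

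| Rates | No correction | 5 tests | 10 tests |
|---|---|---|---|
| 5% vs 15% | 13.6% | 3.4% | 2.8% |
| 8% vs 24% | 33.2% | 12.9% | 8.7% |
| 10% vs 30% | 45.5% | 21.9% | 15.1% |
| 15% vs 45% | 72.7% | 47.9% | 38.5% |
| 20% vs 60% | 91.0% | 75.7% | 67.1% |

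The correction lowers power in every row. How much, and from what starting point, depends on rates the Protocol does not state.

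**Step 4: one concrete result.** Suppose 11/35 versus 3/35 patients have complications. The pooled rate is 14/70 = 0.20, so chi-square = (8/35)² / (0.20×0.80×2/35) = 5.71 and p = 0.017; Fisher p = 0.034. Both are below 0.05. Multiplied by 5 they become 0.084 and 0.17, and the result is non-significant. The risk difference is 8/35 = 22.9 percentage points with standard error √[(0.314×0.686 + 0.086×0.914)/35] = 0.0916, so the unadjusted 95% CI is 22.9 ± 1.96×9.16, about 4.9 to 40.8 points. The interval shows what the corrected p-value would conceal.

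**Step 5: the price of not correcting.** With independent tests and no true differences, the chance of at least one p < 0.05 is 1 − 0.95⁵ = 23% for 5 tests and 1 − 0.95¹⁰ = 40% for 10. This is a real cost, and the reason for a descriptive label.

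**The case against.** The strongest reply has five parts.

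- **The analysis given most weight is not corrected.** The treatment odds ratio for complications is read from an ordinary 95% CI. This stands. A reader might infer that the correction mainly serves to hide harm; the text does not support that. It affects the univariate comparisons and, at most, covariate screening. The treatment term is evidently meant to be in the model whatever the screen finds.
- **Bonferroni is only an example.** This stands. A step-down method would cost somewhat less, but any familywise correction works in the same direction.
- **The power figures rest on assumptions.** This stands. A reader might take 15–22% as the trial's power against any threefold excess. It belongs to 10% versus 30% with about 5 to 10 tests. At 20% versus 60%, uncorrected Fisher power is 91%, which is not low.
- **Correcting safety is a legitimate choice.** In part. Fewer complications with one technique is also a claim of benefit, and not every perioperative characteristic is a harm. That makes the choice a trade-off rather than an error of principle. The equivalence rule is what tips the balance against it.
- **The equivalence rule is the deeper fault.** Largely right. Without any correction, 10% versus 30% would still be missed 43% (chi-square) to 54% (Fisher) of the time. The fix therefore has to address both.

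Two further inferences are tempting and should not be drawn. The closing 0.05 threshold does not contradict the correction: an adjusted p-value is properly compared with 0.05, and that sentence ends the recurrence paragraph. Nor does the correction reach the primary endpoint, since its sentence belongs to the safety comparisons.

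**Conclusion.** The point holds for the univariate safety comparisons. The Protocol applies a multiplicity correction where a missed excess is the costlier error, and does so beside a rule that takes non-significance for complications as equivalence. Under the assumed 10% versus 30%, 35 per arm and Bonferroni over 5 to 10 tests, power is cut by half to two thirds by Fisher's test, and by somewhat less by chi-square. The loss of power is certain in direction; its size cannot be fixed from the Protocol and should be quoted only with its assumptions and range. This is a worthwhile wording change and does not invalidate the trial.

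**What to change.** In the safety paragraph of Study Design for a Randomized Trial:

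1. Remove the p-value correction from the safety comparisons.
2. Report each perioperative and complication comparison as a risk difference or mean difference with an unadjusted 95% CI, labelled descriptive.
3. State that a non-significant safety result, or an odds-ratio CI that includes 1, is not evidence of equivalence; let the interval show which differences remain compatible with the data.

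The cost is wording only, with no change to sample size or data collection. The small downside is that some chance differences will appear among the safety variables (Step 5 of the working) and must be read as descriptive.

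### The covariate rule for the complications model does not exclude variables arising after randomisation, so the treatment OR read for equivalence may not estimate the technique's total effect

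*Protocol*

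**What the plan says.** The section Study Design for a Randomized Trial sets out the safety analysis in consecutive steps.

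- The comparison: "The two Groups will be compared for safety in terms of perioperative characteristics and postoperative complications". Continuous variables are compared by t-test and proportions by Fisher's exact or chi-square test, with a multiplicity correction such as Bonferroni.
- The model: "setting the presence of postoperative complications as dependent variable will be performed, a binary logistic regression will be used".
- The covariates, chosen by a single rule that mentions no time of measurement: "with all the variables significant at the univariate level as predictors".
- The quantity of interest: "The greatest emphasis will be on the dummy variable encoding the different treatments".
- The criteria for equivalence: "the associated coefficient of the regression is not significant from a statistical point view", or an OR close to 1, "in particular the 95% confidence interval contains 1".

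The Background says: "Mesenteric division in CD is challenging because of bleeding that may be difficult to control". It also notes that a thickened mesentery tends to bleed heavily when divided, and gives this as the reason why surgeons commonly divide it close to the bowel. Under Methods, the arms differ in this step. Group A has the mesentery dissected and excised, with a stapled anastomosis. Group B keeps the mesentery, divides it close to the bowel and receives the Kono-S anastomosis, which the aim describes as manual. On access, Methods says only: "The operation could be performed with open or laparoscopic approach".

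**The concern.** In a randomised comparison, variables measured during or after the operation are not confounders of the effect of technique. If the technique changes them and they in turn change the risk of complications, they lie on the causal path. Conditioning on them replaces the total effect of the technique with the part that does not run through them.

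The rule admits every variable that passes the univariate step, whenever it was measured. The only group of variables that the paragraph names besides complications is perioperative characteristics, so the same quantities can be compared as safety results and then used as adjusters.

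This matters because the safety conclusion is read from the treatment coefficient of this model, and a null result counts as equivalence. If one technique caused more complications through bleeding, adjusting for bleeding would hide that harm. Peri-operative safety is part of the stated aim, and postoperative complications are a secondary endpoint.

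The problem is when the covariates are measured, not how they are selected. A list fixed in advance that included intraoperative variables would have the same defect.

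**Working it through.** **The plan's own figure.** The Protocol gives no complication rate or complication OR, so there is none to reproduce here. Its only sample size, 70, is for endoscopic recurrence (45% versus 20%, one-sided 0.05, 75% power). The unpooled formula gives (1.645 + 0.674)² × (0.45×0.55 + 0.20×0.80) / 0.25² = 35.07 per arm, close to 70 in total. It is used below only for the arm size, 70/2 = 35. All complication and bleeding inputs are assumptions.

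**Step 1: full mediation through a binary variable.** Assume 15% complications without heavy bleeding, a bleeding OR of 4, heavy bleeding in 20% of one arm and 40% of the other, and no other effect of technique.

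- Odds without bleeding: 0.15/0.85 = 0.1765. With bleeding: 4 × 0.1765 = 0.7059, a risk of 0.4138.
- Risk at 20% bleeding: 0.80×0.15 + 0.20×0.4138 = 0.203.
- Risk at 40% bleeding: 0.60×0.15 + 0.40×0.4138 = 0.256.
- Total OR: (0.2555/0.7445) / (0.2028/0.7972) = 1.35.
- OR given bleeding: 1.00, by assumption, because bleeding is the only route.

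Over bleeding of 15–20% versus 35–50% and bleeding ORs of 3–6, the extremes are:

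- 20% versus 35%, OR 3 (risk with bleeding 0.3462): 0.1892 versus 0.2187, total OR 1.20.
- 15% versus 50%, OR 6 (risk with bleeding 0.5143): 0.2046 versus 0.3321, total OR 1.93.

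**Step 2: partial mediation and direction.** A large simulated sample (400,000) used one standardised perioperative variable M, shifted by technique by a given number of SDs. M has a log OR of 0.8 per SD on complications, the risk in the reference arm is about 22%, and technique may also have a direct effect.

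| Shift of M (SD) | Direct log OR | Total OR | OR with M in model |
|---|---|---|---|
| 0.5 | 0 | 1.43 | 1.00 |
| 0.8 | 0 | 1.78 | 1.01 |
| 0.8 | +0.3 | 2.32 | 1.36 |
| 0.8 | +0.8 | 3.59 | 2.24 |
| 0.8 | −0.3 | 1.35 | 0.74 |
| 0.8 | −0.6 | 1.03 | 0.55 |
| 0.8 | −1.2 | 0.59 | 0.30 |
| −0.5 | +0.8 | 1.43 | 2.23 |
| 0 | +0.8 | 2.02 | 2.21 |

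The OR moves towards 1 when the mediated and direct effects agree or there is no direct effect (rows 1–4). When they oppose, it moves away from 1 or crosses it (rows 5–8). The last row is non-collapsibility alone: M is unaffected by technique and the shift is small.

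**Step 3: trial size.** With 35 per arm, a 0.8 SD shift, and M entered only if univariately significant at 0.05 (3,000 simulated trials each):

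| Direct log OR | M enters | Non-significant without M | Non-significant under the rule |
|---|---|---|---|
| 0 | 84% | 81% | 95% |
| +0.3 | 90% | 66% | 92% |
| +0.8 | 94% | 31% | 71% |

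For the Step 1 central case at 35 per arm, the figures are about 92% without adjustment and 96% under the rule. For the upper corner (15% versus 50%, OR 6) they are about 79% and 96%.

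**The case against.** Several points on the other side are fair.

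- **The Protocol names no covariates for this model.** Perioperative characteristics appear in the between-group comparison and are not declared to be the candidate list. Bleeding and operating time are not listed as collected variables. This stands, but it does not clear the rule, which takes all significant variables and excludes none. That is a rule the Protocol fixes, not a detail it leaves open.
- **The arm with more bleeding is not stated.** The mesentery is divided in both arms, so 20% versus 40% is an assumption and could be reversed. This stands; only the size and sign of the illustration depend on it.
- **Entry is conditional.** If the Bonferroni-type correction also governs the univariate screen, which the text leaves unclear, then with ten tests assumed bleeding enters in about 28% of central-case trials, against about 60% at 0.05. The exact figures depend on the univariate test used. The problem becomes less frequent but remains.
- **In the central case the conclusion hardly changes** (92% versus 96%), because reading non-significance as equivalence is already very permissive with 35 per arm. That is a separate defect. The added effect is large only when the mediated effect is strong.
- **The unadjusted Fisher or chi-square comparison of complications is unaffected.** True, but the Protocol puts its emphasis on the model.

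A reader might infer that adjustment necessarily pulls the OR towards 1. Step 2 shows that it need not, and the two arms differ in both mesenteric handling and anastomosis, so effects could oppose. A reader might also infer that the technique determines the approach used. Methods allows open or laparoscopic surgery for the operation in general and ties neither to an arm.

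**Conclusion.** The concern holds in limited form. Followed literally, the rule can adjust the safety OR for consequences of the technique, and that OR then need not estimate the technique's total effect on complications. The bias is towards 1, and so towards a claim of equivalence, if the perioperative variable carries harm in the same direction as any direct effect. Otherwise the OR can move away from 1 or across it.

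The size cannot be derived from the Protocol. Under the assumed inputs with full mediation, total ORs of 1.20 to 1.93 (central 1.35) become 1.00; that 1.00 is an assumption, not a finding. Under partial mediation in the same direction, 2.32 becomes 1.36 and 3.59 becomes 2.24. Bleeding has support in the Background; operating time is only plausible.

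The point concerns one model for a secondary endpoint. It should not be read as covering the Cox models for recurrence, because the univariate rule is stated only for the complications model. It is worth correcting because the affected OR decides the safety conclusion and the remedy is nearly free.

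**What to change.** Replace the covariate rule in Study Design for a Randomized Trial with a statement to this effect: the complications model always contains treatment; its other covariates are limited to variables known before randomisation, named in advance (for example age, sex, smoking and centre); perioperative variables such as blood loss, operating time and the approach used are reported by arm as outcomes only; and the safety conclusion rests on the treatment OR from this baseline-only model. If adjustment for approach is wanted, use the intended approach, recorded before allocation is known.

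The same restriction can be written for the Cox models as a precaution.

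The cost is one sentence, plus one CRF field if the intended approach is used. The model can then no longer serve as a search for intraoperative risk factors. That analysis can be reported separately, labelled exploratory, with no equivalence conclusion drawn from its treatment coefficient. The change does not repair the reading of non-significance as equivalence, which needs its own correction.
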